10.2 Minimed 780G insulin pump information

The MiniMed 780G system (Medtronic Diabetes, Northridge, CA) is a CE-marked AHCL system manufactured by Medtronic (16). The MiniMed 780G system is an automated insulin delivery system continuously anticipates insulin needs, adjust insulin delivery and correct high glucose levels automatically while helping to protect the user from low glucose levels as well.

10.1 Guardian 3 and Guardian 4 sensor and receiver

Guardian 3 (17) and Guardian 4 are CE-marked products commercially available by prescription, indicated for patients with T1D. The sensors are both approved for non-adjunctive use, meaning that they can be used to make daily diabetes treatment decisions. The difference between them is that Guardian 4 does not require any calibration during the use, whether Guardian 3 requires calibration 2-3 times daily with a finger prick glucose measurement. The sensor data are stored locally in the pump without internet connection. Data from the pump will be uploaded to the local research server and to the participant's eCRF.

11. Study medication

11.1. Glucagon, GlucaGen®, Novo Nordisk, ATC code H04AA01

Please refer to the medication summary attached, appendix 2 for further details including adverse reaction profile (section 4.8).

In this study, the native glucagon powder (GlucaGen®, Novo Nordisk, Bagsværd, Denmark) will be used and will be dissolve 10 mins before administration.

The product is commercially available by prescription and indicated for participants with T1D. The recommended glucagon dose for severe hypoglycemia is 1 mg administered as a subcutaneous or intramuscular bolus. The administration may be repeated once if lack of clinical response. In this study, glucagon is delivered as a single dose of 150 µg. The total daily glucagon dose will therefore not exceed 1.0 mg per day.

The effects of glucagon are not expected to extend beyond the course of the actual study days. Accordingly, no post-study follow-up is planned, but participants are encouraged to contact the sponsor if they experience or suspect any adverse events to the study medication in the 24 hours following discharge from the research unit. This also applies to participants who discontinue study participation.

Glucagon is ordered via the hospital's pharmaceutical service associated with the pharmacy of the Capital Region. Batch number, date of expiration and the amount used to fill the pump is noted in the participant's eCRF, see section 18 (Source data).

12. Endpoints

12.1 Primary endpoint

- Difference in percentage of time in target glucose range (PG: 3.9 - 10.0 mmol/l) during and for 1-hour after dynamic physical exercise (_{0 min to +105 min}) between visits B and C.

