In recent years, a number of studies have successfully demonstrated that subcutaneous (s.c.) low-dose glucagon can be utilized to effectively treat insulin-induced and exercise-induced mild hypoglycemia in people with T1D (13–15). Likewise, s.c. infusion of low-dose glucagon in dual-hormone AHCL systems has shown promising results in people with T1D (9).

This will be the first feasibility/pilot study to evaluate the use of glucagon provision for **hypoglycemia prevention** during exercise in people with type 1 diabetes using AHCL therapy; the **“HYPO-AVOID”** study. The results of this research may contribute useful data that helps identify glycaemic management strategies that encourage patient safety, and greater exercise participation in people with T1D.

2. Hypothesis

We hypothesize that low-dose glucagon administered s.c. before aerobic exercise is superior to no glucagon regarding glucose control around exercise in people with T1D using AHCL therapy.

3. Study objective

To compare the effect of low-dose glucagon (single 150 µg dose) administered immediately before aerobic exercise versus a control trial without glucagon on glucose responses during and after exercise in individuals with AHCL-treated T1D.

4. Study design

The HYPO-AVOID study consists of a screening visit (visit A) and two additional study visits (visit B and visit C) completed in a sequential order. During study visit B (detailed in section 9), participants will receive s.c. administration of 150 µg glucagon prior to a 45-min moderate intensity continuous exercise session and subsequently continue into a 1-hour post-exercise observation period. During study visit C the exact same procedures will be followed with the omission of glucagon.

5. Subject selection

The HYPO-AVOID study will include individuals with AHCL-treated (Minimed Medtronic 780G) T1D, and the participants will be recruited from the clinic at Steno Diabetes Center Copenhagen.

A written participant information will be handed out along with the brochure: "Forsøgspersoners rettigheder i et sundhedsvidenskabeligt forskningsprojekt".

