5.3 Withdrawal criteria

- Pregnancy (or desire for pregnancy) during the study
- Lack of compliance to any of the important study procedures in the discretion of the investigator
- Withdrawal on the participant's request will be accepted at any time without further justification

Withdrawal does not affect the person's statutory patient rights.

6. Screening

After having received a written and oral informed consent, participants will complete a screening visit that reviews the inclusion and exclusion criteria.

At the screening visit a urine sample will be analyzed for albumin/creatinine ratio and U-HCG (for women with childbearing potential). A blood sample will be analyzed for Hemoglobin A1c (HbA1c), hemoglobin, c-peptide, creatinine, eGFR, ALAT, potassium, sodium, TSH, cholesterol, triglycerides, VLDL, LDL and HDL. ECG, blood pressure, and heart rate will also be measured. Participants will also perform a Cardiopulmonary Exercise Test (CPET) to volitional exhaustion on a workload controlled cycle ergometer. If the participant has recently undertaken a CPET as part of their inclusion in the previous clinical trial at SDCC and reports having no overt changes to their habitual fitness routine, the data from this will be used. Please refer to appendix 1 for a thorough breakdown of both the CPET and moderate intensity exercise test protocols and procedures.

If the participant is eligible for the study, baseline characteristics will be obtained which include sex, age, race, diabetes duration, duration of insulin pump use, insulin pump settings, duration of Continuous Glucose Monitoring (CGM) use, CGM values from the previous 2 weeks, allergies, medical history incl. diabetes late complications, medications, educational status, occupational status, hypoglycemia awareness status, height, weight, physical activity status. All the data will be registered in the electronic case report form (eCRF) for each study participant.

If participants are not eligible to participate in the study, the results of abnormal tests, including positive pregnancy test, will be reported to the participant.

7. Randomization and blinding

This is a two period, crossover interventional study, in which there will be no randomization or blinding.

8. Pre-study procedures

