Participants must refrain from alcohol consumption and strenuous physical exercise 24 hours before the study visit. Participants will also be instructed not to administrate insulin boluses 4 hours prior to the start of the study visit. Conservative administration of glucose tablets prior to study initiation will be allowed to avoid hypoglycemia.

Individuals will be instructed to avoid hypoglycemia (defined as a sensor value and/or finger prick value $< 3.9 \text{ mmol/l}$) 24 hours before each study visit. Hypoglycemia will be avoided by frequently measuring their plasma glucose (PG) and by setting the CGM low alarm to 4.5 mmol/l. If the participant has a low alarm on the CGM, it should always be ensured by Blood Glucose Monitoring (BGM). CGM data for the previous 24 hours will be evaluated on each study day to check for episodes of hypoglycemia. If hypoglycemia ($< 3.0 \text{ mmol/l}$) has been present, the study visit is postponed for at least one day.

9. Study visit procedures

Arrival and preparation:

In-clinic phase:

- Participants will arrive at the research facility at Steno Diabetes Center Copenhagen in the morning following an overnight fast (incl. coffee, medicine and tobacco). Conservative administration of glucose tablets prior to study initiation will be allowed to avoid hypoglycemia.
- A urine HCG test will be performed for all female subjects with childbearing potential. If the test is positive, the primary investigator will inform the subject of the test result and the visit will be cancelled.
- A peripheral venous catheter will be inserted in the antecubital vein to draw blood.
- 15 mins before exercise, the target glucose level will be increased to 8.3 mmol/L in the AHCL system until 15 mins after end of exercise.
- Venous blood glucose sampling will be taken in 15-min intervals from -45 to -15 mins, 5-min intervals from -15 to +60 mins and 15-min intervals from +60 to +105 mins. Samples will be analyzed immediately to determine blood glucose concentrations and later to characterize the metabolomic, hormonal and physiological responses.

Intervention and exercise:

- Immediately before exercise start ($t = 0$), 150 μg s.c. glucagon will be administrated in the abdominal area at visit B. No glucagon will be given at visit C.
- Subsequently, participants will start exercising on an ergocycle with moderate intensity (60% of $\text{VO}_2\text{-max}$, which is available from the CPET) for 45 mins.

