12.2 Secondary endpoints

- Difference in incidence rate of hypoglycemic events ($PG < 3.9 \text{ mmol/l}$) $(0 \text{ min to } +105\text{min})$ between visits B and C
- Difference in time (min) to hypoglycemia ($PG < 3.9 \text{ mmol/l}$) $(0 \text{ min to } +105\text{min})$ between visits B and C
- Difference in percentage of time below target glucose range ($PG < 3.9 \text{ mmol/l}$) $(0 \text{ min to } +105\text{min})$ between visits B and C
- Difference in percentage of time above target glucose range ($PG > 10.0 \text{ mmol/l}$) $(0 \text{ min to } +105\text{min})$ between visits B and C
- Difference in incidence rate of hyperglycemia ($PG > 10.0 \text{ mmol/l}$) $(0 \text{ min to } +105\text{min})$ between visits B and C
- Difference in nadir PG concentration $(0 \text{ min to } +105\text{min})$ between visits B and C
- Difference in peak PG concentration $(0 \text{ min to } +105\text{min})$ between visits B and C
- Difference in incremental peak PG concentration $(0 \text{ min to } +105\text{min})$ between visits B and C
- Difference in mean PG concentration $(0 \text{ min to } +105\text{min})$ between visits B and C
- Difference in PG Area Under the Curve (AUC) $(0 \text{ min to } +105\text{min})$ between visits B and C
- Difference in standard deviation in PG concentrations $(0 \text{ min to } +105\text{min})$ between visits B and C
- Difference in coefficient of variation in PG concentrations $(0 \text{ min to } +105\text{min})$ between visits B and C

13. Statistical considerations

To our knowledge, this is the first study to evaluate the glucose effects of s.c. injection of glucagon around exercise in individuals with AHCL-treated T1D. This is a proof of concept study to assess the use of low-dose glucagon in persons type 1 diabetes performing exercise during treatment with a hybrid closed-loop system with a control arm as a comparator on a sub-group of the full participant cohort. As such, no power calculation has been performed. The sample size of 16 participants has been chosen from a feasibility perspective. It is anticipated that at least 10 of whom will proceed to complete the control arm for comparative purposes in this proof-of concept study.

14. Safety and risk assessment

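### PG at t=0 is not fixed or matched between visits B and C and no analysis is named: prespecify a t=0-adjusted estimate for mean, AUC and nadir PG, and use it only as sensitivity for the range percentages

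*Combined protocol and SAP*

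**What the plan says.** Section 12.1 defines the primary endpoint as "Difference in percentage of time in target glucose range (PG: 3.9 - 10.0 mmol/l) during and for 1-hour after dynamic physical exercise", compared between visits B and C. Section 12.2 adds, among others, "Difference in nadir PG concentration" and "Difference in mean PG concentration", together with AUC and peak, all from 0 to +105 min. Only "Difference in incremental peak PG concentration" appears to refer to a baseline, and its reference value is not defined.

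Section 7 states that "there will be no randomization or blinding". Visit B (glucagon) comes before visit C (control), and Section 4 says of the second: "During study visit C the exact same procedures will be followed with the omission of glucagon".

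Sections 8 and 9 standardise conditions:
- an overnight fast, and no insulin bolus in the 4 h before the visit;
- no alcohol or strenuous exercise for 24 h;
- a CGM low alarm at 4.5 mmol/l, and postponement after a value below 3.0 mmol/l in the previous 24 h;
- a pump setting: "15 mins before exercise, the target glucose level will be increased to 8.3 mmol/L in the AHCL system".

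Glucose tablets are permitted before the visit, with no amount given. PG is sampled at t=0 at both visits.

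Section 13 gives 16 participants, chosen for feasibility, and adds: "It is anticipated that at least 10 of whom will proceed to complete the control arm". It names no test, model, covariate or interval.

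**The concern.** The plan standardises the conditions before exercise but not PG itself. A pump target changed 15 minutes beforehand is not a required PG at t=0, and the postponement rule looks back over 24 h.

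Pairing removes stable differences between people. It does not remove a difference in starting PG between one person's two visits. Because the order is not randomised, nothing balances such a difference in expectation, and 10 pairs leave room for chance.

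Every endpoint window opens at 0 min, so starting PG is part of mean, AUC and nadir. A gap at t=0 would be counted as glucagon effect or would mask it. With no model named in an open-label study, the decision to adjust could also be taken after the data are seen, and the reported estimate could then depend on that decision.

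**Working it through.** **Inputs.** From the documents: n = 10 pairs (16 planned), a window of 105 min, exercise of 45 min, the sampling times, and carry-forward of the nadir after PG below 3.9 mmol/l. The documents give no starting PG, SD, exercise fall, glucagon rise or power calculation, so there is no plan figure to reproduce. All glucose inputs below are assumptions.

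**Step 1: how a gap passes through.** Let starting PG differ by g = 1 mmol/l between visits. Let PG fall linearly over 45 min and then stay level for 60 min. Let the fall grow by k mmol/l per mmol/l of starting PG; k > 0 represents a pump that makes the fall steeper from higher starts.
- Mean: g × [1 − k × (0.5×45 + 60)/105] = 1 − 0.786k
- AUC: 105 × mean shift = 105 − 82.5k
- Nadir (end of exercise): 1 − k

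| k | Mean (mmol/l) | AUC (mmol/l·min) | Nadir (mmol/l) |
|---|---|---|---|
| 0 | 1.00 | 105 | 1.00 |
| 0.3 | 0.76 | 80 | 0.70 |
| 0.6 | 0.53 | 56 | 0.40 |

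Carry-forward flattens low profiles and generally trims these values further.

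**Step 2: simulated trials of 10 pairs.** Mean start 6.5 to 8.5 mmol/l, between-person SD 1, within-person SD 0.5, 1 or 2, mean fall 2 or 3, glucagon rise 0, 1.5 or 3, carry-forward applied. Visit C starts 1 mmol/l higher.
- Fall independent of start: the unadjusted difference moves by 0.6 to 1.0 (mean) and 0.5 to 1.0 (nadir). Its 95% CI covers the no-gap effect in 42–91% and 48–92% of trials.
- Same setting, adjusted: it moves by at most 0.18 (mean) and 0.25 (nadir), with coverage 92–96% and 90–96%.
- Fall steeper from higher starts (k = 0.3 to 0.6): the unadjusted difference moves by 0.49 to 0.74 (mean) and 0.34 to 0.62 (nadir). A similar model with mean fall 2.5 gave 0.42 to 0.78 and 0.22 to 0.71, with an adjusted residual of at most 0.14.

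**Step 3: chance gaps.** For within-person SD s, P(|mean gap| > 1) = 2 × [1 − Φ(1/(s√(2/n)))]. With n = 10 and s = 1, s√(2/n) = 0.447, 1/0.447 = 2.24, and P = 2.5%. For s = 1.5 and 2, P = 13.6% and 26.4%. With 16 pairs the three values are 0.5%, 5.9% and 15.7%. At s = 0.5 the probability is negligible.

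**Step 4: cost in precision.** Let r be the correlation between the outcome difference and the t=0 difference. The approximate CI width ratio, adjusted to unadjusted, is

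√{(1 − r²) × [1 + (1 + n·g²/(2s²))/(n − 3)]} × t(n−2)/t(n−1).

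- n = 10, g = 0: √(8/7) × 2.306/2.262 = 1.09, times √(1 − r²). The interval is 9% wider at r = 0, breaks even at r = 0.40, and is 6% and 22% narrower at r = 0.5 and 0.7.
- n = 10, g = 1, s = 0.5: n·g²/(2s²) = 20, so √(1 + 21/7) × 1.019 = 2.04, times √(1 − r²). At r = 0.4 this is 1.87; at r = 0 it is 2.04.

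Simulated widths at s = 1 without a gap: 8–32% narrower (mean) and 4–36% narrower (nadir) with k = 0; with k > 0, nadir runs from 14% narrower to 3% wider. With a gap at s = 0.5: 62–85% wider (k = 0).

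**Step 5: range percentages.** A low start adds time below 3.9 and a high start adds time above 10.0. The simulated slope of time in range on the t=0 difference ran from +17 to −4 points per mmol/l. With fall 3 and a held rise of 3, the effect itself was +15 points at start 7.5 and −12 at start 8.5. With a rise, a gap and s = 1, the adjusted estimate had a 16–64% larger SD and still missed the no-gap effect by 3 to 14 points.

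**Step 6: peak.** If PG only falls, peak is the t=0 value and the slope is about 1, so adjusted peak nearly repeats incremental peak. With no glucagon rise, the adjusted interval covered in only 76–98% of trials.

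**The case against.** The strongest reply is that this is a feasibility study with no power claim, that the primary estimate does not change, and that the root gap is the absence of any analysis in Section 13. All of that is true. It limits the weight of the point and means the change can sit inside a general analysis paragraph. It does not remove the point: Section 2 states a superiority hypothesis, and the covariate is already measured.

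A second reply is that the pump responds to glucose and dampens a starting difference. This stands in part: it lowers the pass-through and shrinks the precision gain, and the ranges above include it. A third is that benefit depends on an unknown within-person SD. At SD 0.5, adjustment gains little, and it is costly if the visits differ.

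A reader might infer more than the documents support:
- **That starting PG does differ between visits.** Nothing shows this, and the standardisation in Sections 8 and 9 may limit its variability.
- **That the plan rules out adjustment.** It is unspecified, not excluded.
- **That glucose tablets go unrecorded because Section 18 does not list them.** That list follows a sentence on routine-care databases. It also omits the glucagon batch details that Section 11.1 says are recorded, so it is not a full inventory.
- **That the primary endpoint or peak should be adjusted too.** Steps 5 and 6 argue against both.

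**Conclusion.** The point holds as a worthwhile, low-cost improvement. PG at t=0 is neither fixed nor matched in the available text, and a text for Appendix 1 that set a starting glucose would change this. Under assumed inputs, a 1 mmol/l gap moves unadjusted mean PG by about 0.5 to 1.0 mmol/l (AUC in proportion) and nadir by about 0.3 to 1.0, less where the fall is steeper from higher starts. Adjustment removes most of this, leaving up to about 0.25 mmol/l in nadir because of carry-forward.

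Confidence in the size is moderate, since no glucose input comes from the documents. Adjustment deals only with measured starting PG; other period effects of the fixed order stay inseparable from treatment.

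**What to change.** In Section 13:
1. For mean, AUC and nadir PG, prespecify a regression of the within-person B−C outcome difference on the B−C difference in t=0 PG, not centred at the sample mean. The intercept, which is the effect at equal starting PG, is the estimate. Report the unadjusted paired difference alongside. State that the t=0 sample is drawn before the injection, because Section 9 does not give the order.
2. For percentage of time in, below and above range, keep the unadjusted paired difference as the main estimate and prespecify the same regression as sensitivity only.
3. For peak, rely on incremental peak and state t=0 PG as its reference, in place of an adjusted peak.
4. Tabulate t=0 PG by visit.

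This takes a few sentences and no new sampling. It uses one degree of freedom with about 10 pairs. At within-person SD 1 mmol/l without a gap, the adjusted interval runs from about 30% narrower (up to 36% for nadir in the most favourable setting) to about 3% wider. At SD 0.5 with a 1 mmol/l gap it can be about 90% wider. Hypoglycaemia incidence, time to hypoglycaemia, SD and CV may also depend on starting PG and are not covered by this change.

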12.2 Secondary endpoints

- Difference in incidence rate of hypoglycemic events ($PG < 3.9 \text{ mmol/l}$) $(0 \text{ min to } +105\text{min})$ between visits B and C
- Difference in time (min) to hypoglycemia ($PG < 3.9 \text{ mmol/l}$) $(0 \text{ min to } +105\text{min})$ between visits B and C
- Difference in percentage of time below target glucose range ($PG < 3.9 \text{ mmol/l}$) $(0 \text{ min to } +105\text{min})$ between visits B and C
- Difference in percentage of time above target glucose range ($PG > 10.0 \text{ mmol/l}$) $(0 \text{ min to } +105\text{min})$ between visits B and C
- Difference in incidence rate of hyperglycemia ($PG > 10.0 \text{ mmol/l}$) $(0 \text{ min to } +105\text{min})$ between visits B and C
- Difference in nadir PG concentration $(0 \text{ min to } +105\text{min})$ between visits B and C
- Difference in peak PG concentration $(0 \text{ min to } +105\text{min})$ between visits B and C
- Difference in incremental peak PG concentration $(0 \text{ min to } +105\text{min})$ between visits B and C
- Difference in mean PG concentration $(0 \text{ min to } +105\text{min})$ between visits B and C
- Difference in PG Area Under the Curve (AUC) $(0 \text{ min to } +105\text{min})$ between visits B and C
- Difference in standard deviation in PG concentrations $(0 \text{ min to } +105\text{min})$ between visits B and C
- Difference in coefficient of variation in PG concentrations $(0 \text{ min to } +105\text{min})$ between visits B and C

13. Statistical considerations

To our knowledge, this is the first study to evaluate the glucose effects of s.c. injection of glucagon around exercise in individuals with AHCL-treated T1D. This is a proof of concept study to assess the use of low-dose glucagon in persons type 1 diabetes performing exercise during treatment with a hybrid closed-loop system with a control arm as a comparator on a sub-group of the full participant cohort. As such, no power calculation has been performed. The sample size of 16 participants has been chosen from a feasibility perspective. It is anticipated that at least 10 of whom will proceed to complete the control arm for comparative purposes in this proof-of concept study.

14. Safety and risk assessment

If PG drops below 3.9 mmol/l or the participant experiences unbearable symptoms of hypoglycaemia, 15 g of oral glucose will be administered, and subsequent close monitoring of PG will be ensured. The investigator can, at any given time, choose to discontinue the study visit if deemed necessary for safety reasons. Likewise, individuals can withdraw from the study at any given time.

In general, exercise is associated with a risk of hypoglycemia for people with T1D. In this study, some participants might experience an episode of mild hypoglycemia (PG level between 3.0 to 3.9 mmol/l). Symptoms of mild hypoglycemia (e.g. shakiness, dizziness, sweating, palpitations, hunger or headache) are relatively modest and previously experienced by all people with T1D. The risk of severe hypoglycemia during the study is very low, as the participants will be closely monitored with frequent glucose measurements and continuous clinical evaluation. Moreover, an IV catheter is maintained throughout the study visit which will enable fast elevation of PG if needed.

Administration of glucagon carries a small risk of transitory side effects with symptoms such as nausea and headache being the most frequent. However, as dose sizes in this study are small, the frequency of these side effects is expected to be low and the intensity mild.

The amount of blood extracted during the study visit equals about 250 ml (a regular blood donation amounts to approximately 500 ml), which is not expected to cause any adverse effects.

Performing venipuncture may inflict a short pain and a risk of a small hematoma, and there is a minimal risk of infection at the puncture site.

With regards to all other planned study procedures, the risk of complications or adverse events is negligible and certainly outweighed by the benefits of this study.

A study investigator, who also is a medical doctor, will always be present at the research facility during conduct of the study.

15. Adverse event management

Definition of adverse event (AE):

Any untoward medical occurrence in a patient or clinical investigation subject administering/using a product (which does not necessarily have to have a causal relationship with this treatment). An adverse event can therefore be any unfavorable and unintended sign (including an abnormal laboratory finding), symptom, or disease temporally associated with the use of a product, whether considered related to the product.

Hyperglycemia and hypoglycemia handled by the safety procedures are not considered as AE.

Definition of serious adverse event (SAE):

An adverse event that results in death, is life threatening (an event in which the patient was at risk of death at the time of the event; not an event which hypothetically might have caused death if it was more severe), requires inpatient hospitalization or results in prolongation of existing hospitalization, results in persistent or significant disability/incapacity or is a congenital anomaly/birth defect.

Definition of serious adverse reaction (SAR):

A SAE for which a causal relationship to the study medication is at least possible (i.e. a causal relationship is conceivable and cannot be dismissed).

Definition of suspected unexpected serious adverse reaction (SUSAR):

A SAE which is unexpected and regarded as possibly or probably related to the trial/study product by the investigator. To evaluate whether the adverse reaction is to be expected, investigator shall refer to section 4.8 in the medication summary (Appendix 2).

Classification of intensity of AE:

Mild: No or transient symptoms, no interference with the patient's daily activities.

Moderate: Marked symptoms, moderate interference with the patient's daily activities.

Severe: Considerable interference with the patient's daily activities, which the patient find unacceptable.

Classification of causality of an AE:

Related: A causal relationship is conceivable and cannot be dismissed.

Not related: The event is most likely related to etiology other than the trial product

Final outcome classification of an AE:

Recovered/resolved: The patient has fully recovered, or the condition has returned to the level observed at trial entry.

Recovering/resolving: The condition is improving, and the patient is expected to recover from the AE.

Recovered/resolved with sequelae: The patient has recovered from the condition, but with lasting effect due to a disease, injury, treatment or procedure.

Not recovered/not resolved: The condition of the patient has not improved and the symptoms are unchanged, or the outcome is not known.

Fatal: This term is only applicable if the patient died due to the AE.

Unknown: This term is only applicable if the patient is lost to follow-up.

Investigations and potential treatment of an AE:

Dependent on the investigator's evaluation. Participants experiencing AEs will be monitored until satisfactory stabilization and/or full recovery.

Reporting of AE, SAE, SAR and SUSAR:

All events meeting the definition of an AE will be collected and reported. The causality is evaluated by the investigator. AEs will be collected from the beginning of the study day (visit B) until 12 hours after initial dosing of glucagon as the effects of glucagon are not expected to extend beyond this time frame. SAEs, SARs will initially be reported to the sponsor within 24 hours after the investigator has become aware of the adverse event. All follow-up data will be described in detail in a SAE-formula and subsequently given to the sponsor within 24 hours of obtaining the new knowledge. Previous non-serious AEs that becomes SAEs will follow the reporting of SAEs. It is the sponsor who will evaluate if the reported SAE and SAR are a SUSAR.

Sponsor will ensure that all information on SUSARs that are fatal or life-threatening is recorded and reported to the Danish Health and Medicines Authority (web-based form) as soon as possible and no later than seven days after the sponsor becomes aware of such possible side effects. Within eight days after reporting, sponsor will provide the Danish Health and Medicines Authority with all relevant information about the sponsor's and investigator's response to the alert and consequences for the further course of the study conduct.

All other SUSARs will be reported to the Danish Health and Medicines Authority within 15 calendar days after sponsor becomes aware of them. Moreover, a safety report will be compiled each year, which will be sent to the Regional Scientific Ethics Committee and Danish Medicines Agency.

Reporting at the end of the study:

All AEs and SAEs will be included and uploaded in the results section of the study EudraCT (<https://eudraact.ema.europa.eu/>). The link to this report will be sent to the Danish Health and Medicines Authority and the Regional Scientific Ethics Committee within 12 months after the last participant has completed the project. SARs are reported to the Danish Health and Medicines Authority and the Regional Ethics Committee annually.

16. Extraction of biological samples

A research biobank will be established for all blood samples that are collected from the HYPO-AVOID study. At each sampling timepoint there will be drawn approximately 5,8 mL of blood; 0,5 mL will be disposed as waste, 0,3 mL for quantification of plasma glucose and lactate and 5 ml for biobanking. In total 250 mL blood will be drawn. All blood samples are designated with a code that cannot be directly referred to

the individual. Only PG, lactate and ketone bodies are analyzed immediately. The research unit has several freezers that are only used to store samples from different projects. The freezers are locked and can only be accessed by staff members from the research unit. Furthermore, the freezers are continuously monitored and alert a responsible for any significant temperature changes. The frozen blood samples will be analysed for metabolomic and hormones within 10 year after the study end, i.e. before 01/01/2032. If there is any remaining material left, the samples will be stored for future analyses after approval from the Capital Region's Videnscenter for Dataanmeldelser. If remaining material will be used for future studies, we will apply for approval by the Regional Scientific Ethical Committee.

The analyses will be performed at the SDCC CoreLab, Steno Diabetes Center Copenhagen and at Department of Biomedical Sciences, Endocrinology Research Section, University of Copenhagen.

17. Use of data from patient health records

Data from patient health records will be used during the screening process. By signing the informed consent, the participant grants access to information in the medical health record relevant to participation in the study. The access applies for the primary study investigator, sponsor (and representatives) and potential regulatory authorities (for quality control). After receiving the informed consent, relevant information from the medical health records will be revisited during the screening visit.

18. Source data

A separate electronic case report form (eCRF, REDCap) will be prepared for each study participant. Patient information will be retrieved from routine-care hospital databases (Sundhedsplatformen and Carelink). Information on diagnosis, age, sex, diabetes duration, insulin pump settings, medical history, medications, blood test results and ECG will be collected.

Glucose measurements are documented by the source files generated from the respective apparatus (YSI measurements from Yellow Spring Instruments 2900 STAT Plus). Data from devices without long-term internal memory (e.g. blood pressure apparatus) will be transferred directly to the eCRF.

A monitoring plan will be established in collaboration with the GCP-unit at Copenhagen University Hospital and includes full monitoring of informed consent, serious adverse events, inclusion and exclusion criteria. Source data will also be verified by the GCP-unit according to the monitoring plan.

19. Handling of personal data

The study will be carried out in accordance with the Helsinki Declaration after approval by the Regional Scientific Ethical Committee, Region H's Data Protection Unit (Videnscenter for Dataanmeldelser) and the Danish Medicines Agency.

All information on study subjects is protected according to law on processing of personal data and the law of health.

All health-related matters and sensitive personal data will be handled in accordance with the data protection act (databeskyttelsesloven) and GDPR (databeskyttelsesforordningen).

The electronic study database (REDCap) is password protected and located on the hospital network server which is continuously backed up. The electronic file with the key linking the CPR-number and all other information that is personally identifiable will be kept on a locked drive created for that purpose only. Only the study sponsor and investigators will have access to the study database.

All health-related matters and sensitive personal data (CRF, blood test result etc.) will be depersonalized. All participants will be given a number referring to their personal information, which will be stored securely and separately. Adequate anonymization of all personal data during data processing and publication will be ensured.

Data will be stored in coded form in 10 years after last participant last visit (LPLV) according to recommendations from the Data Protection Agency.

Study data may be shared with cooperating partners outside Steno Diabetes Center Copenhagen, but only in a form in which all personally identifiable information has been removed. Data will only be shared with cooperating partners outside SDCC after acceptance from “Videnscenter for Dataanmeldelser”.

20. Time schedule

First participant first visit (FPFV) is expected in June 2022, while last participant last visit (LPLV) is expected in Marts 2024. Data analysis will be completed within 12 months after LPLV.

21. Project economy

The study is initiated by the investigators. All investigators are employed at Steno Diabetes Center Copenhagen or University of Swansea. None of the investigators have personal financial interest in the conduct or the outcome of the project.

The primary investigator, [name], is not restricted by any means and no external parties hold rights to the study results. If further funding is achieved, the national ethics committee will be notified and the protocol, the protocol resume and the participant information documents will be updated.

22. Remuneration

Participants do not receive remuneration for study participation.

23. Insurance

Participants are covered by the state compensation scheme ('Patienterstatningsordningen' og 'Ordningen om erstatning for lægemiddelskader').

24. Dissemination of study results

Data will be processed and merged into at least one scientific article and published in an international peer-reviewed scientific journal. Positive, negative and inconclusive results will be published as soon as scientifically justifiable. The latest study protocol will be published at www.clinicaltrials.gov.

25. Ethical considerations

The risk of side effects when participating in this study is expected to be modest as elaborated on in the section 14 (Safety and risk assessment). A number of studies have previously demonstrated safety and efficacy of the low-dose glucagon for preventing and treating hypoglycemia, and glucagon has been well tolerated, safe and effective in all previous studies.

The study will be carried out in accordance with the Declaration of Helsinki and the principles of good clinical practice after approval by the Regional Scientific Ethics Committee and the Danish Medicines Agency. The study will be registered at www.clinicaltrials.gov. The GCP Unit, Copenhagen University Hospital, is responsible for study monitoring which includes full monitoring of informed consent, power of attorney and SAEs. Further, the participants agree to allow direct access to their source data/documents, including patient journals, during monitoring, auditing and/or inspection by an ethics committee, the Danish

